### 7.2. *Magnetic Resonance Imaging*

Following the 1st Photomedex helmet application, a baseline MRI will be performed, at the earliest opportunity, as soon as the subject is able to lay flat for 1 hour and the scanner is available for use. If the subject is admitted as an inpatient the scan will take place at Lunder 6 on the MGH Main Campus. If the subject is discharged from ED Observation prior to the first MRI, then the baseline MRI will take place at the Martinos Center at the Charlestown Campus. It is anticipated that the MRI will take place within 24-48h hours after enrollment and the scanning protocols themselves will take approximately 60 minutes to perform. Taking into account any necessary set up time before, during and after scanning the total time for the MRI will be approximately 60-90 minutes. If the subject is unable to undergo research-related imaging, this will be deferred until it is safe and feasible. This baseline MRI is performed

following the first application of light therapy because of the need to deliver light therapy as soon as possible after injury, and the clinical challenges of performing MRI within the first 12 hours. A designated study staff member will be responsible for gathering post-procedure follow-up data on the subject. The subjects will be followed until discharge.

Imaging protocol (for baseline and post-treatment imaging):

Subjects will be asked to lie still in a supine position for the duration of the imaging session. Head motion will be minimized during image acquisition by the use of a dedicated head coil with holder.

The MRI protocol may include the following sequences:

- 1) Localizer/Auto-aligned scout
- 2) High resolution T2 weighted imaging
- 3) FLAIR (Fluid attenuated inversion recovery) imaging
- 4) High resolution 3D T1 weighted isotropic imaging
- 5) Susceptibility-weighted imaging (SWI)
- 6) Diffusion tensor imaging (60 encoding directions)
- 7) BOLD EPI functional MRI for the evaluation of resting state functional connectivity (FC) within and between motor, visual, auditory, dorsal attention, executive control, salience and default mode networks.
- 8) Arterial Spin Labeling (ASL) brain perfusion imaging.

No contrast agent or other pharmacological substance other than ones clinically required for the subject will be given.

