#### **4. Recruitment Procedures**

Patients will be approached for enrollment by members of the research team, which include clinical research coordinators and research managers in addition to the PI and other study physicians. Recruitment and enrollment will likely occur in the Emergency Department as it is preferred that the study procedures begin as soon as possible after consent has been obtained. EPIC and other relevant patient databases will be used by qualified research and clinical staff (research coordinators, managers, and study physicians) to electronically identify patients who may be potential candidates for the study. The trauma alert/stat pager may also be used to identify potential subjects by qualified study staff.

We will recruit subjects with head injury according to our inclusion/exclusion criteria. Depending on the type of head injury patients may be admitted as an inpatient or admitted to the ED observation unit.

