## 7. **Research Design and Methods**

A member of the study staff familiar with the subject population will evaluate eligibility based on the approved inclusion/exclusion criteria, using patient charts. If a subject is eligible a physician on the study staff will approach the subject and/or surrogate for informed consent (please see consent procedures for more details). Demographic and clinical data will be collected during the acute hospitalization in accordance with the common data elements proposed by the TBI Common Data Element Project [29]. A drop point for deterioration for

withdrawing a subject will be a change in the GCS of greater than 2 from the previous exam.

After informed consent has been obtained, the subject will be randomized. All subjects will undergo either treatment or sham (placebo) procedures. In the sham procedure, the helmet will be placed on the patient but the LEDs will not be activated. The randomization will be set up so subjects are assigned sequentially into one of 9 groups with 10 subjects in each group. Within each group, the subject will be assigned randomly to either treatment or sham with an allocation ratio of 1:1. Once the first 10 subjects have been enrolled and have finished treatment (or sham) a DSMB (see detailed description under data safety and monitoring) will go over all of the safety data presented and make a recommendation on the continuation of the study. Subsequent DSMB meetings will take place once per year

If the subject is admitted to the ICU, he/she, will be treated according to the ICU standard of care procedures.

- Standard of care procedures include:
- Monitoring of O2/CO2 levels;
  - Avoiding hypotension;
  - Maintaining temperature within normative range;
  - Adjusting cervical collar placement if necessary;
  - Repeat CT scan if necessary;
  - Bed placement at > 30 degrees while in the ICU
  - Sedation and analgesia using recommended agents

If the subject is admitted to the ED Observation Unit, he/she will be treated according to the ED standard of care procedures.

The application of the Photomedex helmet will be in addition to but will not change the standard of care.

The following table summarizes the timing and specific assessments to be conducted in this study:

ASSESSMENTS	PRE-PROCEDURE	PROCEDURE	FOLLOW UP
Eligibility Assessment	X		
Informed Consent Form a	X		
Demographics, including date of birth, gender, and race and ethnicity	X		
Medical History	X		

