### **7.3. Follow Up**

Follow up visits will be coordinated by the study staff with the subject and/or surrogate.

Additional MRI scans will be performed at approximately 14-21 days and 3 months after injury for image analysis (see Section 7.2 for Imaging Protocol). At day 7 a follow-up phone call will be made to check on the subject after discharge for symptoms reporting. Clinical follow-up visits will take place at approximately 14-21 days, 3 months and 6 months post-injury. The 6 month follow up can be completed in person or over the phone since it does not require in person physical evaluation. A follow-up phone call will also be performed at day 7 and at 12 months.

For subjects who are discharged from the ED's 24-hour Observation Unit, the same follow up procedures will apply. Additionally, subjects in ED Observation who only received 1 helmet application will have up to 2 additional helmet application(s) performed by study staff at a follow up appointment. Throughout the study duration, subjects may be contacted by phone, email or mail by clinical research staff for study related reasons.

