## **11. Risk Benefit Analysis**

### **11.1. *Known and Anticipated Risks***

We anticipate the risk to the subjects due to participation in this study to be low. Subjects who have satisfied the inclusion/exclusion criteria as outlined in the protocol will be eligible for enrollment. All subjects will be treated according to the standard of care guidelines for their condition according to the medical staff. For the experimental portion of the procedure, after consent has been obtained, subjects will undergo approximately 20 minutes of exposure to the Photomedex Helmet for at least 2 time points and up to 3 time points. The first helmet application will take place in the inpatient unit or in the ED observation unit. If the subject is admitted as an inpatient he/she may have up to 2 additional helmet applications no sooner than 12 hours after the previous helmet application. If the subject is discharged from either the inpatient unit or the ED observation unit prior to his/her 2nd helmet application, he/she will have up to 2 additional helmet applications no sooner than 12 hours after the previous helmet application arranged either through a follow up visit.

In order to optimize the LLLT, we would like to shave the head. This will be optional to the surrogate/subject and will be explained at the time of informed consent. There is a slight potential risk of a small cut to the head during shaving of the head. In addition, there is a small amount of radiant heat that is generated by the Photomedex helmet. The helmet will be efficiently cooled with fans but depending on the skin and hair color of the subject the temperature of the scalp may be raised enough to be perceived as warmth. In addition, the subject's core temperature will be monitored and in the unlikely event that the temperature increases more than 0.5 C the helmet will be removed.

Following initial exposure to the Photomedex Helmet, a baseline MRI will be performed at the earliest opportunity as soon as the patient is able to lay flat for 1 hour and the scanner is available for scheduling. If the subject is admitted to an inpatient unit, he/she will have the first MRI scan in Lunder 6 at the MGH Main Campus. If the subject is discharged from the ED Observation unit, he/she will have the first MRI scan at the Martinos Center in Charlestown.

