For subjects admitted to the inpatient unit, there is a small risk of complication associated with moving the subject from the ICU to radiology for MRI. The most common complications are related to inadvertent dislodgement of tubes and lines or related to temporary disconnection from the mechanical ventilator. These complications are inherent in any travel out of the ICU. If the risk of travel complications is deemed by the clinical (non-study) team to be too high, MRI for the purposes of this study will be deferred until a later date. The FDA considers investigations using MRI software and hardware to be non-significant risk, as long as they are operated within

FDA specified parameters. All MRI studies will adhere to the FDA approved for the Siemens 3T system used in this research. These safety parameters include static magnetic field, time varying magnetic fields (dB/dt), specific absorption rate (SAR), and acoustic noise levels.

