Light Therapy for Moderate Traumatic Brain Injury

NCT02233413

Statistical Analysis

6.26.20

Statistical Analysis

All statistical analyses were performed using R Language for Statistical Computing (version 3.6.0). Differences and relations were considered statistically significant at $p < 0.05$. All results are presented as mean + standard deviation (S.D.) unless noted otherwise. Baseline differences across groups were compared via using one-way ANOVA for continuous variables (e.g., Age, RPQ scores) and via Chi-Square test for categorical variables. To test neuroreactivity of LLLT via its effect on the diffusion tensor parameters, we used a linear mixed effect (LME) model with treatment (light therapy vs. sham) and time point (acute, early sub-acute, late sub-acute) as fixed effects, and tract and time point nested within each patient as random effects. All patients with at least one MRI were included in this analysis. Conformity of the data to statistical assumptions were checked by investigating QQ plots of the data. LME models, which are akin to multiple regression models that can account for correlations due to repeated measures, have several advantages in this context. LME modeling allowed us to pool all our data --- i.e., across treatment groups and three time points, as well as across all 18 tracts --- to examine relationships robustly. Moreover, because the LME model allows partially repeated measures, it can accommodate data from subjects with missing timepoints (e.g., missing MRI sequences). In addition, the LME model treats each timepoint as a separate variable. Therefore, any baseline difference in DTI parameters across the LLLT and sham groups did not confound the overall analysis enabling one to robustly identify differences in DTI parameters across the treatment groups while explicitly accounting for repeated measurements, within-tract and within-subject correlations, and missing time points.

A similar LME model (treatment group and time point as fixed effects, and patient as a random effect) was used to test for the effect of LLLT on clinical symptoms). The p values for the fixed effects in the LME model were calculated using type III analysis of variance table with Satterthwaite's degrees of freedom method.

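### Does the DTI model need a care-pathway term because the first MRI is done at different sites for inpatients and ED Observation patients?

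*Protocol*

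**What the plan says.** Protocol section 7.2 (Magnetic Resonance Imaging) assigns the first scan by location of care. For inpatients: "If the subject is admitted as an inpatient the scan will take place at Lunder 6 on the MGH Main Campus". For those who leave ED Observation before the scan: "then the baseline MRI will take place at the Martinos Center at the Charlestown Campus". Section 11.1 repeats the rule: "If the subject is discharged from the ED Observation unit, he/she will have the first MRI scan at the Martinos Center in Charlestown". Pathway is linked to the injury in section 4: "Depending on the type of head injury patients may be admitted as an inpatient or admitted to the ED observation unit".

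Section 7 sets up nine sequential groups of ten and adds "Within each group, the subject will be assigned randomly to either treatment or sham with an allocation ratio of 1:1". It mentions no stratification by pathway or site.

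For later imaging, section 7.3 says "Additional MRI scans will be performed at approximately 14-21 days and 3 months after injury for image analysis" and names no site. Section 11.1 refers to a single platform: "All MRI studies will adhere to the FDA approved for the Siemens 3T system used in this research". Section 7.2 gives one imaging protocol for baseline and post-treatment scans.

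The SAP's linear mixed model for the diffusion parameters has "treatment (light therapy vs. sham) and time point (acute, early sub-acute, late sub-acute) as fixed effects". Its random effects are tract and time point within patient. It has no term for pathway, site or scanner, and it writes out no treatment-by-time interaction.

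**The concern.** Diffusion measures can differ between scanners, and here the scanner at the first MRI partly follows a variable that itself reflects the type of injury. The random effects take up such a difference as variance, but they do not remove it from a between-arm comparison. If one arm happened to hold more inpatients, its acute DTI values could differ for reasons unrelated to light therapy. Neither document says that scanner mix will be shown by arm or time point, so a reader could not tell.

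Two features sharpen the worry. The baseline MRI follows the first helmet application, so no untreated scan is available as a covariate. The SAP also states that baseline DTI differences did not confound the analysis. Treating each time point as a separate variable does not undo a chance imbalance in the acute scans. At stake are the precision and the interpretability of the DTI result, which is the outcome used for the sample-size calculation.

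**Working it through.** **Inputs.** From Protocol section 9: effect 25% of the mean, CV of FA 40%, 41 per group. From section 3: 90 subjects, so 45 per arm. From section 7: 1:1 allocation. From the SAP: significance at 0.05. Assumed, because the documents do not give them: two-sided testing, 80% target power, the site or pathway difference *s* (in SDs), and the share *p* of subjects in one pathway.

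**The plan's own figure.** The standardised effect is 0.25/0.40 = 0.625 SD. The usual rule for 80% power gives 16 × (0.40/0.25)² = 40.96, so 41 per group and 82 in total. The stated size reproduces.

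**Variance added by an omitted difference.** Omitting the term multiplies the variance of a single-scan contrast by 1 + p(1 − p)s². Power is from the noncentral t distribution at 45 per arm, with effect 0.625/√(1 + p(1 − p)s²).

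| Difference, % of mean FA | s (÷ 40%) | Variance factor, p = 0.5 | Power without the term |
|---|---|---|---|
| 0 | 0 | 1.000 | 83.5% |
| 2 | 0.05 | 1.0006 | 83.4% |
| 5 | 0.125 | 1.004 | 83.3% |
| 10 | 0.25 | 1.016 | 82.9% |
| 20 | 0.5 | 1.063 | 81.2% |

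**Cost of the term.** With pathway in the model there are 87 residual degrees of freedom and a small loss from chance imbalance. Averaged over that imbalance, power is 83.0%, which is 0.4 points below the unadjusted 83.5% when pathway is irrelevant. The two approaches break even at s = 0.218 for p = 0.5 (0.218 × 40% = 8.7% of mean FA) and at s = 0.272 for p = 0.2 (10.9%). At s = 0.5 the term gains 1.8 points at an even split and 1.0 point at 20:80.

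**Bias and type I error.** A simulation of the acute contrast (41 per arm, even split, 4,000 runs per setting, s from 0.25 to 1.0) gave mean unadjusted estimates between −0.004 and 0.005 SD when there was no effect. Rejection rates were 4.5% to 5.1%.

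**Chance imbalance.** With 45 per arm, the exact binomial chance of a gap of at least 20 percentage points in pathway share is 7.3% at 50:50 and 2.5% at 20:80. A 20-point gap moves the contrast by 0.2 × s. For s from 0.05 to 0.5 that is 0.01 to 0.10 SD, or about 2% to 16% of 0.625.

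**What the SAP model actually tests.** The table describes one scan with one value per patient. The SAP model pools three time points, and the site rule is documented only for the first scan. With three complete, equally weighted scans, a shift confined to the first enters the patient mean at one third: 0.5/3 = 0.167. The SD of that mean is √((1 + 2ρ)/3), where ρ is the within-patient correlation (assumed). For ρ = 0.5 this is 0.816 and the shift is 0.20 SD. For ρ = 0.8 it is 0.931 and the shift is 0.18 SD. Both lie below the break-even value.

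**The case for a change.** The best argument for a change is asymmetry. The term costs about 0.4 points of power if pathway is irrelevant, but it could recover much more if pathway matters a great deal. In the simulation at 41 per arm with a 1.0 SD difference, power was 70.7% without the term and 78.8% with it. With no untreated scan, pathway is one of the few injury-related variables available for adjustment. A difference that persists across all three visits would not be diluted by pooling, and missing follow-up scans would weaken the dilution of a first-scan shift.

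Part of this stands. The SAP's assurance about baseline differences does not cover a chance imbalance in site or pathway, and a table of scanner and pathway by arm and time point would let readers judge it.

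The rest is weaker. A 1.0 SD difference is 40% of mean FA, larger than the whole 25% planning effect. The 40% CV is a between-patient figure for the intended population and may already contain pathway variation; if so, the inflation above counts it twice. The case for a scanner effect is thin, given one named platform and one imaging protocol.

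Pathway also determines the first site only in part. No site is given for ED Observation subjects scanned before discharge, and imaging may be deferred. Actual scan site is settled after the first helmet application. If treatment altered time to discharge, site could differ systematically between arms, and adding scanner to the main model would then mean adjusting for a post-randomisation variable. The documents give no sign that this happens.

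**Conclusion.** The description is correct: first-scan site partly follows pathway, and the model omits both. No change to the plan follows. Under 1:1 randomisation the omission adds variance without bias. The loss is under 1 point of power for differences up to 0.25 SD and 2.3 points at 0.5 SD (45 per arm, even split). A pathway term improves power only above roughly 0.22 to 0.27 SD, or 9% to 11% of mean FA, and the documents do not show that the difference is that large. A shift limited to the first scan would probably fall below that threshold once three scans are pooled. Statisticians could reasonably choose either model.

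These conclusions rest on assumed differences, pathway shares and within-patient correlations. A very large, persistent pathway difference would favour adjustment. The SAP is written in the past tense, so if results are already known, a pathway-adjusted fit would belong beside the main model as a sensitivity analysis labelled post hoc. Reporting scanner and pathway mix by arm and time point is optional detail that analysts can supply without altering any result.

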### **7.3. Follow Up**

Follow up visits will be coordinated by the study staff with the subject and/or surrogate.

Additional MRI scans will be performed at approximately 14-21 days and 3 months after injury for image analysis (see Section 7.2 for Imaging Protocol). At day 7 a follow-up phone call will be made to check on the subject after discharge for symptoms reporting. Clinical follow-up visits will take place at approximately 14-21 days, 3 months and 6 months post-injury. The 6 month follow up can be completed in person or over the phone since it does not require in person physical evaluation. A follow-up phone call will also be performed at day 7 and at 12 months.

For subjects who are discharged from the ED's 24-hour Observation Unit, the same follow up procedures will apply. Additionally, subjects in ED Observation who only received 1 helmet application will have up to 2 additional helmet application(s) performed by study staff at a follow up appointment. Throughout the study duration, subjects may be contacted by phone, email or mail by clinical research staff for study related reasons.

## **8. Concomitant Medication**

Each subject's concomitant medication regimen before the start of the trial is to be documented. Concomitant medications are to be recorded on the appropriate case report form (CRF).

## **9. Statistical Methods**

In this pilot study, the study size is limited by number of recruitable patients admitted to MGH emergency department. Based on prior-year admission records, the itemized inclusion/exclusion criteria, and an assumed 80% consent rate, we estimate an average enrollment of 1 patient per week.

The sufficiency of these enrollments toward powering the primary hypothesis (DTI outcome measure) is presented below. These calculations require an assumption of the acute LLLT therapeutic effect size, which is unknown and cannot reasonably be estimated from either the preclinical data or the clinical stroke studies. Our analysis is based on an assumed effect size of 25%.

The coefficient of variation for fractional anisotropy (FA) is based on data from a cohort of 12 mild to moderate TBI patients scanned using quantitative MRI [30]. For this cohort, FA was measured in 16 regions of the brain. The coefficient of variation (CV), defined as the ratio of mean to the standard deviation, was 53.45%. However, this study included mild to moderate. With the more narrow inclusion of moderate TBI, we estimate a FA CV of 40% (based on clinical and research experience of the investigators, and knowing that the CV for healthy volunteers is 25%). The required sample size for detecting changes in FA associated with acute LLLT [31] is then 82 (41 patients in each group). We note that other diffusion parameters (mean diffusivity, axial diffusivity, and radial diffusivity) featured much lower CV, and would be sufficiently powered with this sample size.

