## Protocol Synopsis

### Low-level light therapy (LLLT) with near infrared light emitting diodes in patients with moderate traumatic brain injury

Trial Population	Males and females 18 years and older admitted to the Emergency Department (ED) or Trauma Service with a head injury requiring hospital admission as either an inpatient or for observation.
Investigational Product	Custom designed Photomedex helmet with LED cluster heads emitting near infrared light.
Control	Randomized subjects assigned to the placebo procedure (non-activated Photomedex helmet)
Trial Design	Double-blinded placebo controlled study
Primary Objective	Safety and feasibility of using the Photomedex helmet for LLLT and quantify the response to LLLT using magnetic resonance imaging and clinical outcome measures.
Number of Subjects	Up to 90 subjects at Massachusetts General Hospital will be enrolled into the trial.
Key Inclusion Criteria	

• At least 18 years old;

• Injury within 72 hours at the time of consent;

• Head injury requiring hospital admission;

• A Glasgow Coma Scale (GCS) score of 9-12 or 13-15 with abnormal imaging.

Key Exclusion Criteria	

• Need for emergency neurosurgical intervention (including placement of intracranial pressure monitoring devices or drainage catheters);

• Hemodynamic instability as determined by the clinician;

• History of any of the following: (i) brain tumor; (ii) prior TBI occurring within the past year and requiring hospital admission; (iii) a new diagnosis within the past year of either stroke or epilepsy; (iv) an established diagnosis of any of the following neurodegenerative diseases: Alzheimer's, Picks, Parkinson's, Lewy body dementia,

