## 2. **Specific Aims**

The goal of this research is to assess PBM using LLLT to improve outcomes in subjects with moderate traumatic brain injury (TBI). In this study we use the definition of TBI as described by the DoD: GCS between 9-12 or 13-15 with an abnormal head CT.

The specific aim of this study is to determine the feasibility of PBM with near infrared light emitting diodes (LEDs) using the Photomedex Helmet and to quantify the response to LLLT using magnetic resonance imaging (MRI) and clinical outcome measures. We hypothesize that the Photomedex helmet will successfully deliver LLLT and that we will be able to quantify the response to LLLT through imaging and clinical outcome measures.

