**Table 1: Selection Criteria**

Inclusion Criteria	I1. At least 18 years old; I2. Injury within 72 hours at the time of consent; I3. Head injury requiring hospital admission;; I4. A Glasgow Coma Scale (GCS) score of 9-12 or 13-15 with abnormal imaging.
Exclusion Criteria	E1. Need for emergency neurosurgical intervention (including placement of intracranial pressure monitoring devices or drainage catheters); E2. Hemodynamic instability as determined by the clinician; E3. History of any of the following: (i) brain tumor; (ii) prior TBI occurring within the past year and requiring hospital admission; (iii) a new diagnosis within the past year of either stroke or epilepsy; (iv) an established diagnosis of any of the following neurodegenerative diseases: Alzheimer’s, Picks, Parkinson’s, Lewy body dementia, Huntington’s, amyotropic lateral sclerosis, spinocerebellar ataxia, vascular dementia, HIZ-associated dementia, dementia due to metabolic causes (Addison, Cushing, hypothyroidism, renal failure, prophyrias, Wilson, mitochondrial diseases, Wernicke-Korsakoff syndrome, and dementia of unknown etiology. E4. Pregnancy (all women of child-bearing age will need to have a negative urine pregnancy test prior to the start of the interventional portion of the study); E5. Electrical implants such as cardiac pacemakers or perfusion pumps; E6. Ferromagnetic implants such as aneurysm clips, surgical clips, prostheses, artificial hearts, valves with steel parts, metal fragments,

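### Does lowering the FA coefficient of variation from 53.45% to 40% undermine the sample size of 82?

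*Protocol*

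**What the plan says.** Protocol Section 9 calls the study a pilot whose size is limited by the number of recruitable patients. It then announces a power argument: "The sufficiency of these enrollments toward powering the primary hypothesis (DTI outcome measure) is presented below". It says the therapeutic effect size is unknown and cannot reasonably be estimated, and assumes 25%.

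For variability it cites a cohort of 12 mild to moderate TBI patients: "For this cohort, FA was measured in 16 regions of the brain". It continues: "The coefficient of variation (CV), defined as the ratio of mean to the standard deviation, was 53.45"%. (The definition is inverted in the text; the figure is used as SD over mean.) It then lowers the value: "With the more narrow inclusion of moderate TBI, we estimate a FA CV of 40"%, citing the investigators' experience and a CV of 25% in healthy volunteers. The conclusion reads: "The required sample size for detecting changes in FA associated with acute LLLT [31] is then 82 (41 patients in each group").

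The Synopsis sets the ceiling: "Up to 90 subjects at Massachusetts General Hospital will be enrolled into the trial". Table 1 defines who may enter: "I4. A Glasgow Coma Scale (GCS) score of 9-12 or 13-15 with abnormal imaging". Section 2 gives the matching definition of TBI: "GCS between 9-12 or 13-15 with an abnormal head CT".

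**The concern.** The only CV tied to a patient dataset is 53.45%, and the planning value is about a quarter lower. In variance terms the reduction is 44%. No patient data are cited for 40%, and 40% is almost exactly the value at which the planned numbers suffice.

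The stated reason, narrower inclusion, is open to question because the trial still admits GCS 13-15 when imaging is abnormal. Section 9 gives no alpha, no power and no sensitivity range.

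If the true CV were nearer 53.45%, a reader told that 82 was the required size might take a null FA result as evidence against a 25% effect when the comparison had little better than even odds of detecting one.

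**Working it through.** **Inputs.** From Section 9: effect 25% of mean FA; planning CV 40%; cited CV 53.45%; healthy-volunteer CV 25%; 41 per group. From the Synopsis and Section 7: up to 90 subjects at 1:1, so 45 per group. The 0.05 level is in the SAP. Two-sided testing and 80% power are assumed, because together they reproduce 41 per group; a one-sided test gives 32 and 90% power gives 54. No dropout allowance is applied, as in Section 9.

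**The plan's own figure.** The standardised difference is 0.25/0.40 = 0.625.
- Rule of thumb: n per group = 16 × (0.40/0.25)² = 40.96, so 41.
- Normal approximation: 2 × (1.960 + 0.842)² × (0.40/0.25)² = 40.19, so 41.
- Noncentral t: 42.

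The stated 82 reproduces.

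**Power for a 25% difference as the CV varies** (noncentral t, two-sided 0.05):

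| CV | 82 subjects | 90 subjects |
|---|---|---|
| 30% | 96% | 97% |
| 35% | 89% | 92% |
| 40% | 80% | 83% |
| 45% | 70% | 74% |
| 50% | 61% | 65% |
| 53.45% | 55% | 59% |

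**Break-even CV.** The standardised difference giving 80% power is 0.6263 with 41 per group and 0.5972 with 45. Dividing 0.25 by each gives 39.9% and 41.9%.

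**At a CV of 53.45%.**
- Rule of thumb: 16 × (0.5345/0.25)² = 73.14, so 74 per group (148 in total). The normal approximation gives 72 (144) and noncentral t gives 73 (146).
- Difference detectable with 80% power: 0.5345 × 0.6263 = 33% with 82; 0.5345 × 0.5972 = 32% with 90.
- Variance ratio: (0.40/0.5345)² = 0.56, hence the 44% reduction.

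**How firm is 53.45%?** Section 9 does not say whether it describes spread between patients, between the 16 regions, or both pooled. If it includes between-region spread, it is not the SD for a per-patient comparison. If it is purely between patients (assuming normality, 12 independent values and a known mean), the chi-square 95% interval on 11 degrees of freedom runs from 0.5345 × √(11/21.92) = 38% to 0.5345 × √(11/3.816) = 91%. That interval contains 40%, and also much worse values. The midpoint of the two cited CVs is (25 + 53.45)/2 = 39.2%.

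**The other assumption.** At a CV of 40% with 82 subjects, power is 61% for a 20% effect and 39% for a 15% effect. The effect size, which the protocol says is unknown, matters about as much as the CV.

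**The case for a change.** The strongest case for a change is that disclosing an estimate differs from disclosing what hangs on it. Section 9 offers 82 as proof of sufficiency, yet one judgement separates about 80% power from about 55%, and even 45% brings power down to 70-74%. With 82 subjects the expected 95% confidence half-width is 17.6% of mean FA at a CV of 40% and 23.5% at 53.45%. In the second case any estimate above about 1.5% (25 − 23.5) would fail to exclude a 25% effect. A conditional sentence would cost almost nothing.

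The sensitivity is real and the figures stand. So does part of the eligibility point: admitting GCS 13-15 makes the cohort less narrow than the word moderate suggests. But Table 1 still excludes GCS 13-15 with normal imaging, so the inclusion may be narrower than that of a mild to moderate cohort; the documents do not give that cohort's imaging criteria. The rationale is partly supported, which is no reason to delete it.

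The rest does not carry to a change. A sample size solved at 40% loses 80% power just above 40% by construction; the cap of 90 supplies the only margin. A reader of Section 9 has every input needed to redo the calculation. How a null result should be read depends on the estimate and standard error obtained, not on the planning CV.

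**Conclusion.** No change to the plan is needed. The 82 is right for its stated inputs, and the trial falls short of no power that it claims, since none is stated. The 40% is a disclosed judgement in a pilot whose size is limited by recruitment. Its effect on power runs in both directions: with 82 subjects, from 96% at a CV of 30% to 55% at 53.45%.

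These figures assume one FA value per patient, an additive 25% difference with a common SD, two-sided 0.05 and complete data. They do not describe the SAP's mixed model over 18 tracts and three time points, which takes in every patient with at least one MRI. Its power cannot be computed, because the documents give no correlations.

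The SAP is written in the past tense, so rewording Section 9 could not affect the design, and it would alter no analysis or result. A two-sided CV range in Section 9, the observed between-patient FA CV, and a 95% confidence interval for the FA effect would help readers. They are optional reporting additions.
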